10.3 Methods of Assigning Subjects to Treatment Groups

Subjects who provide informed consent, complete all screening assessments, meet all eligibility criteria, and are accepted for enrollment into the study will be assigned a unique subject identification number.

Each subject will receive a unique subject number upon entry in the EDC system. In cases when subjects are not eligible for enrollment at the baseline visit (e.g., due to a temporary condition), they will be considered a screen failure. Rescreening of such a subject is allowed upon resolution of the temporary condition. In this case, a new subject number will be assigned, and all screening assessments will be repeated.

All subjects will receive a single Ultherapy treatment on the Octave System – that is, no randomization will be used.

CCI

10.5 Study Treatment

All protocol-specific criteria for the administration of study treatment must be met and documented prior to the start of any study treatment. All treatments with the investigational device will be performed on site by the treating investigator or by delegated and qualified study personnel. Subjects will not be dispensed any investigational material. Any noncompliant subject or site may be discontinued from the study (Section 9.2.6.2 and Section 9.2.7, respectively).

10.5.1 Planned Treatment Procedure and Administration

Subjects in Stage 1 will be enrolled to receive treatment of the brow, upper, mid, and lower face, and neck with one transducer beginning at energy level 4 CCI and one transducer beginning at energy level 2 CCI

Subjects in Stage 2 will be enrolled to receive treatment of the brow, upper, mid, and lower face, and neck with three transducers beginning at energy level 4 CCI and one transducer

[figure not shown]
beginning at energy level 2 CCI In both stages, energy levels can be titrated down at the investigator's discretion.

10.5.1.1 Pre-Treatment Assessments

All subject-related, pre-treatment study activities ([Section 11.1](#)) should be completed prior to administration of pre-treatment medications.

[figure not shown]
10.5.1.2 Pre-Treatment Medications and Procedure

CCI

[figure not shown]

10.5.1.3 *Treatment Region and Administration Procedure*

CCI

[figure not shown]

CCI

10.5.1.3.2 Stage 1 Treatment

CCI

For Stage 1, treatment lines should be administered with the CCI transducers first, followed by the CCI transducer. Treatment with the CCI transducer should begin at energy level 4 CCI and titrated down to energy level 1 CCI at the investigator's discretion. Treatment with the shallow transducer CCI CCI should begin at energy level 2 CCI and can be reduced to energy level 1 (i.e., 0.15 J), at the investigator's discretion.

[figure not shown]
At the investigator's discretion, a line-count range, per treatment zone, is allowed CCI. Each zone must receive at least the minimum number of lines and should not receive more than the maximum number of lines. The investigator will perform an ultrasound scan prior to treatment to determine the presence of soft tissue at the appropriate depth for the intended transducer(s) to be used within each region, according to Inclusion Criteria 4 and 5; the investigator will then record the intended treatment plan on the treatment planning worksheet. Study subjects administered line counts that differ by \pm 10% of the treatment guideline will be categorized as receiving a full treatment and will not be considered protocol deviations CCI.

To ensure appropriate collection of pain data CCI, each treatment zone should receive the full line count with each transducer CCI before moving to the next zone.

Laterality is the subject's right or left.

Investigators will be trained by the sponsor to use Octave System ultrasound imaging to ensure proper treatment is delivered (e.g., contact, depth).

CCI

10.5.1.3.3 Stage 2 Treatment

Stage 2 will not be performed until confirmation is received from FDA that the CCI transducers may be used.

For Stage 2, treatment lines should be administered with the CCI transducers first, followed by treatment with CCI transducer, and lastly with the CCI transducer. Treatment with the three deeper transducers CCI should begin at energy level 4 CCI

CCI [REDACTED]. At the investigator's discretion, each transducer's energy setting can be titrated down to energy level 1 CCI [REDACTED] [REDACTED]. Treatment with the shallow transducer CCI [REDACTED] should begin at energy level 2 CCI [REDACTED] and can be reduced to energy level 1 CCI [REDACTED] at the investigator's discretion.

At the investigator's discretion, a line-count range, per treatment zone, is allowed CCI [REDACTED]. Each zone must receive at least the minimum number of lines and should not receive more than the maximum number of lines. The investigator will perform an ultrasound scan prior to treatment to determine the presence of soft tissue at the appropriate depth for the intended transducer(s) to be used within each region, according to Inclusion Criteria 4 and 5; the investigator will then record the intended treatment plan on the treatment planning worksheet. Study subjects administered line counts that differ by \pm 10% of the treatment guideline will be categorized as receiving a full treatment and will not be considered protocol deviations CCI [REDACTED]

To ensure appropriate collection of pain data CCI [REDACTED] each treatment zone should receive the full line count with each transducer CCI [REDACTED] before moving to the next zone.

Laterality is the subject's right or left.

Investigators will be trained by the sponsor to use Octave System ultrasound imaging to ensure proper treatment is delivered (e.g., contact, depth).

[figure not shown]
CCI

[figure not shown]
Laterality is the subject's right or left.

Treatment should begin with the deepest transducer set initially to energy level 4, except for the CCI
CCI transducer which should start at energy level 2; additional pain medication (Section 10.5.1.2), as well as incremental reduction in energy, is allowed, as necessary, for subject comfort.

CCI

CCI

10.5.2 Selection and Timing of Treatment for Each Subject

At the baseline visit, all enrolled healthy, adult subjects with mild to moderate eyebrow/upper-face laxity and mild to moderate fine lines, wrinkles, and laxity of the face and neck will receive a single Octave-Ultherapy treatment of the full face and neck according to the treatment guidelines presented in [Section 10.5.1.3](#). No additional treatments will be offered under this study protocol.

10.5.3 Treatment Interruption and Modification

If any problems occur during system operation, the treating clinician should take the following immediate action(s): lift the transducer off the subject's skin, press the **Imaging/Ready** button on the handpiece or console to discontinue treatment in progress, and/or press the red emergency **Stop** button to completely halt console operation.

As described in [Section 10.5.1.2](#), should the subject experience escalating pain during the Ultherapy procedure that is not adequately controlled with the previously selected treatment regimen, the investigators may use their discretion to utilize further protocol-specific options to control pain. If the pain experienced by the subject remains intolerable after having administered the maximum allowable limit and type of treatment medications, treatment should be discontinued, and the subject will be followed for safety only.

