Risks of treatment with the second-generation Ulthera Octave System will be minimized or reduced by training the investigational sites and monitoring the subject during the treatment procedure, with careful observation of the subject's pain and skin response to treatment. Previous clinical studies with the Ulthera DeepSEE System have shown the sensory response was tolerable from both the subject's and investigator's perspective.[\[12\]](#) Discomfort was transient, and acute pain resolved within 30 minutes. If the subject is uncomfortable during Octave System treatment, the treating investigator has the option to utilize additional measures to improve tolerability, including additional/different pain medication (e.g., see [Section 10.5.1.2](#)). If treatment remains intolerable after implementation of mitigation measures, the treating clinician must stop administering treatment, for the subject's safety, and the subject will be followed for AEs throughout the study's duration. In the case of an AE report, the subject will be followed until the subject's last study visit, until the AE is resolved or stabilized, the subject is lost to follow-up, or some other resolution of the event occurs.

Considering all risks and benefits of Ultherapy on the Octave System, the potential benefits to physicians and subjects seeking treatment outweigh the potential risks. The benefit/risk ratio of the device is considered acceptable when used on subjects seeking a lift of the eyebrow region and improved appearance of the face and neck.

Additional information on device- and procedure-related contraindications, warnings, and precautions can be found in the current version of the Octave Clinical IFU CCI [REDACTED]

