Subjects who provide informed consent but who do not meet eligibility criteria or who withdraw consent prior to being treated at the baseline visit will be defined as screen failures. The investigator will maintain all source documentation for all subjects who are considered screen failures. Minimal information will be collected in the electronic data capture (EDC) system for screen failures, such as date of informed consent, demographics, and reason for screen failure. In cases where a subject is not meeting eligibility criteria due to a temporary condition, this subject may be rescreened, at the discretion of the treating investigator, upon resolution of the temporary condition.

9.2.6 *Removal of Subjects from Therapy or Assessment*

9.2.6.1 *Treatment Discontinuation*

Investigators will be instructed to immediately pause subject treatment upon the rare occurrence of an intra-procedural adverse event of interest, such as:

1. Second-degree burn/blister;
2. Neurological change, including, for example:
 - Motor (paralysis/weakness/paresis/twitching); or
 - Sensory (changes in vision, hearing, tinnitus).

Additional information, including stopping rules, are described in [Section 9.2.8](#).

If study treatment is discontinued during administration, the investigator will record the reason for treatment discontinuation in the study records. Potential reasons for discontinuation of treatment may include refusal by the subject to receive additional treatment or physician's decision. The investigator should request that a subject discontinuing treatment continue to participate in the study and complete all remaining visits and safety follow-up assessments. For subjects declining continued study participation after treatment discontinuation, additional information regarding subject withdrawal is provided in [Section 9.2.6.2](#).

If the subject experiences escalating pain during the Ultherapy procedure that is not adequately controlled with the initially selected treatment regimen, the investigators may use their discretion to utilize further protocol-specific options to control pain ([Section 10.5.1.2](#)). Attempts should be made to optimize pain medication so that treatment can be completed.

9.2.6.2 *Subject Withdrawal or Discontinuation*

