Each subject will be followed to the end of study, or until the sponsor decides to terminate the study, whichever comes first. The only reasons a subject will not be followed for all scheduled visits include withdrawal of consent, continuous non-compliance with protocol requirements, or loss to follow-up (e.g., moving away from study site; unresponsive to attempts to contact the subject). Additionally, the investigator can discontinue any subject, at any time, if medically necessary.

Subjects have the right to withdraw from the study at any time at their own request without prejudice. In cases of withdrawn consent, data collected until the date consent was withdrawn will be analyzed as recorded.

If a subject does not attend a required study visit, the following actions will be taken:

- The site will attempt to contact the subject at least twice and reschedule the missed visit as soon as possible. Every effort to regain contact with the subject will be made (e.g., telephone contact on different dates/times, registered mail). All contact attempts will be documented.
- If attempts to contact the subject are not successful, the subject will be considered lost to follow-up and discontinued from the study.

The reason for the subject's discontinuation should be documented in the electronic case report form (eCRF). The investigator should make every attempt to complete the recommended follow-up assessments specified for the End of Study/Early Termination visit specified in the Schedule of Events ([Section 11.1](#) and [CCI](#) [REDACTED]), while fully respecting the subject's rights.

In the case of a reported nerve effect leading to paresthesia or weakness, as well as any severe unanticipated AE that is determined to be an AE related to the device treatment, a root-cause investigation will be conducted to determine the cause, the outcome of the event, and status of subject. The investigator and the sponsor will conduct a thorough evaluation of the event. The sponsor will then immediately make a determination if the study should be suspended ([Section 9.2.8](#)).

If a non-serious AE is unresolved at the time of the subject's final study visit, an effort will be made to follow the subject until the AE is resolved or stabilized, the subject is lost to follow-up, or some other resolution of the event occurs. The investigator should make

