All subjects will receive a single, site-administered Ultherapy treatment using the Octave System ([Section 10.5.1.3](#)) on Day 1 (Visit 2). Subject-reported pain associated with treatment will be assessed after completing treatment with each transducer and for each region treated ([Section 11.2.2.3](#)). Importantly, if the subject experiences escalating pain during the Ultherapy procedure that is not adequately controlled with the initially selected treatment regimen, the investigators may use their discretion to utilize further protocol-

specific options to control pain ([Section 10.5.1.2](#)). Due to pre-treatment and intra-procedural medications, subjects must have a driver following the study treatment visit ([Section 10.5.1.2](#)).

Subjects will be contacted by telephone 3, 14, 28, 120, and 150 days after treatment and will be required to present for an unscheduled visit if indicated by safety concerns. [CCI](#)

Safety follow-up will occur until Day 90 ± 7 days or Day 180 ± 14 days for subjects who reconsent, when applicable, for extended participation.

The primary endpoint visit will occur at Visit 3 (Day 90 ± 7 days). Prior to the investigator's skin examination, the subject must wash the treatment area to remove any moisturizers/emolients, makeup, bronzing agents, etc. on the face and/or neck region, if necessary. [CCI](#)

In all cases, even those in which a subject prematurely discontinues the study, a final assessment [CCI](#) should be performed.

11.1.1 *Scheduled Visits*

All scheduled visits and applicable study assessments must occur as noted in [Section 11.1](#)
[CCI](#)

11.1.2 *Unscheduled Visits*

To ensure subject safety, any subject who, for any reason, requires additional follow-up that does not coincide with a scheduled study visit should have that visit recorded as an unscheduled visit, during which concomitant medication/procedures, skin examination, and AEs must be assessed and recorded.

[CCI](#)

An unscheduled visit must be scheduled if information acquired from a subject during a post-treatment phone call requires additional follow-up, as determined by the investigator.

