## 4.2 Intent-to-Treat Population (ITT)

The Intent-to-Treat population (ITT) consists of all subjects who are enrolled.

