#### 6.1.1 Primary Effectiveness Endpoint

##### 6.1.1.1 Primary analysis

The primary endpoint of the study is the proportion of treated subjects with eyebrow lift by comparing photographs taken at Day 90 (post-treatment) with baseline (pre-treatment) photographs.

Each independent evaluator will assess “Eyebrow Lift”, “No Eyebrow Lift” or “Cannot Evaluate” between Photograph 1 (baseline) and Photograph 2 (post-baseline). Photograph 1 will be identified, and the independent evaluators will be blinded to the random distribution of treated versus untreated status of the comparator Photograph 2 (i.e., Day 90 post-treatment among treated subjects or post-baseline for untreated individuals). Lift will be declared if at least two blinded evaluators indicate “Eyebrow Lift” for the comparator photograph. In case at least two evaluators declare a photograph as not assessable (i.e., “Cannot Evaluate” is ticked), the corresponding lift score over all evaluators will be set to missing for the primary analysis. In case one evaluator rates a photograph as “Cannot Evaluate” and the other two evaluators disagree, the overall lift score will be set to “No Lift”.

The point estimate for the proportion of subjects fulfilling the primary endpoint will be described by frequency statistics for the ITT subset.

[figure not shown]
Effectiveness is established if:

[figure not shown]
- A. the point estimate is  $\geq 65\%$  and
- B. the lower bound of the one-sided 95% Wilson CI is  $> 50\%$ .

In addition, the proportion of untreated individuals fulfilling the primary endpoint will be calculated. It is expected that the point estimate for the proportion of untreated individuals is  $< 50\%$ .

Missing data, including a missing primary endpoint assessment in subjects with unacceptable (i.e. unassessable) or missing photographs at baseline or Day 90, will be imputed by multiple imputation. In case of complete data, no multiple imputation will be performed and the primary analysis is based on complete data for the ITT.

Imputation is done 50 times using a fully conditional specification logistic regression method, as implemented in SAS PROC MI with statement FCS LOGISTIC, and will use the investigational site and the baseline characteristics age and BMI as independent variables.

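### Protocol 10.5.3 conflicts with 9.2.6.1, 9.2.6.2 and 11.1 on follow-up after a stop for pain, so a Day 90 lift can go missing and be imputed mainly at the fully treated rate

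*Protocol*

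**What the plan says.** Four places in the protocol bear on follow-up after a session is stopped for pain.

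- **10.5.3:** if pain remains intolerable after the permitted medication, "treatment should be discontinued, and the subject will be followed for safety only".
- **9.2.6.1:** the investigator should ask a subject whose treatment is discontinued to "continue to participate in the study and complete all remaining visits and safety follow-up assessments". The section names subject refusal and physician's decision as possible reasons, and goes on to discuss escalating pain.
- **9.2.6.2:** "The only reasons a subject will not be followed for all scheduled visits include withdrawal of consent", continuous non-compliance or loss to follow-up. The investigator may also discontinue a subject if medically necessary. A pain stop is not listed.
- **11.1:** in all cases, "even those in which a subject prematurely discontinues the study, a final assessment" should be performed. What it contains is redacted.

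The analysis side is in the SAP. Section 4.2: "The Intent-to-Treat population (ITT) consists of all subjects who are enrolled". Section 6.1.1.1: a missing primary assessment, including one due to "missing photographs at baseline or Day 90, will be imputed by multiple imputation". The imputation model "will use the investigational site and the baseline characteristics age and BMI as independent variables". SAP 6.4.1 applies this to treated subjects with a missing outcome and makes no exception for an incomplete session.

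**The concern.** The same subject falls under two follow-up rules. If a site takes safety-only follow-up to mean that effectiveness photographs are not needed, the protocol itself creates a missing primary outcome, and it does so in subjects who received less treatment. They remain in the ITT. Most observed outcomes come from completed sessions, and the imputation model cannot tell a completed session from a stopped one. The imputed values therefore follow mainly the fully treated lift rate.

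The study has one arm and is judged against fixed thresholds: a point estimate of at least 65% and a one-sided 95% Wilson lower bound above 50%. No control arm would absorb an upward shift, and the result could depend on which section a site follows.

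**Working it through.** **1. The plan's own figure.** Inputs from Protocol 13.1 and SAP 3: 72% responder rate, the dual success rule, at least 85% power, 40 evaluable subjects. With n = 40 the smallest passing count is 26 (26/40 = 65.0%, Wilson lower bound 52.0%). The binomial probability of 26 or more of 40 at 72% is 87.6%. Scanning upward from n = 20, 40 is the first size to reach 85% (84.9% at 38, 82.2% at 39). The stated sample size reproduces, and this point does not change it.

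**2. Path to the primary analysis.** Stop for pain → safety-only follow-up read as no photographs → Day 90 lift missing → subject kept in the ITT → value imputed from site, age and BMI. Only the second step is a matter of interpretation. The rest is as written.

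**3. Size of the shift.** Let N = 50 (planned enrolment), k = pain-stopped subjects without Day 90 photographs, p = lift rate in fully treated subjects and q = lift rate in partly treated subjects. The documents give neither k nor q, so both are assumed ranges.

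- All-treated rate = ((50 − k)·p + k·q) / 50
- Rate after imputation ≈ p
- Overstatement ≈ k·(p − q) / 50

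For example, with k = 5, p = 0.72 and q = 0.4: (45 × 0.72 + 5 × 0.4)/50 = 34.4/50 = 68.8%, an overstatement of 3.2 points.

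| p | k | q = 0 | q = 0.2 | q = 0.4 | Overstatement, points |
|---|---|---|---|---|---|
| 72% (plan) | 1 | 70.6% | 71.0% | 71.4% | 1.4 to 0.6 |
| 72% (plan) | 3 | 67.7% | 68.9% | 70.1% | 4.3 to 1.9 |
| 72% (plan) | 5 | 64.8% | 66.8% | 68.8% | 7.2 to 3.2 |
| 67% (assumed) | 3 | 63.0% | 64.2% | 65.4% | 4.0 to 1.6 |
| 67% (assumed) | 5 | 60.3% | 62.3% | 64.3% | 6.7 to 2.7 |

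At 72%, only k = 5 with q = 0 falls below 65%, by 0.2 points. The 67% rows show a fully treated rate close to the threshold.

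**4. Chance of success at p = 72%.** With n = 50 the rule needs 33 lifts (66.0%), and the probability is 86.4% when all 50 are fully treated and observed. If five are pain stops and are observed, it is 49.7% if none of them lifts and about 71% if they lift at half the rate (36%). With three the figures are 67.5% and about 78%. Under the planned imputation, simulation gives about 83–88% for k from 1 to 10. The simulation used 50 imputations drawn from the observed rate, which simplifies the site, age and BMI model.

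**5. One data set.** Take 31 lifts in 45 observed subjects plus 5 missing. Imputation gives 68.9% with a lower bound of 56.7%, a pass. If all five had no lift, the result is 31/50 = 62.0%, which fails the 65% condition.

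**The case against.** The strongest reply is that 10.5.3 is the outlier. Sections 9.2.6.1, 9.2.6.2 and 11.1 all point to continued attendance, and the SAP's disposition section expects treated subjects at every visit to Day 90 or Day 180 unless they discontinue the study, with no safety-only track. No passage says photographs are omitted, and the schedule of events is redacted. This stands: a reader might infer that these subjects certainly go unphotographed, but the documents show only that they may.

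A reader might also count Protocol 6.3 as a further contradiction, because after an intolerable treatment "the subject will be followed for AEs throughout the study's duration". That sentence keeps the subject in the study and does not exclude effectiveness assessment, so it is not one.

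A third inference is that the conflict would turn a failing trial into a passing one. At the plan's 72%, five of the six scenarios with three or five stops stay above 65%. At 67%, three stops with 40% partial lift gives 65.4%, which still meets the point-estimate rule. Pain stops may also be rare, since energy can be lowered and medication optimised, and a subject stopped after the brow was finished may have had full brow treatment.

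Finally, the prespecified worst-case analysis counts every missing lift as no lift, and treatments stopped for pain are listed. Together these would expose the problem. However, the worst-case analysis does not decide success and mixes in subjects lost for unrelated reasons. The per-protocol and observed-case analyses leave out these subjects when their lift is missing.

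**Conclusion.** The conflict between 10.5.3 and 9.2.6.1, 9.2.6.2 and 11.1 is real and should be resolved. Its effect on the primary proportion is possible but not established. It requires that sites read 10.5.3 as omitting photographs, that more than one subject is affected, and that partly treated subjects lift less often than fully treated ones. With three to five affected subjects of 50 and 0–40% lift among them, the overstatement is about 1.9 to 7.2 points at the plan's 72% rate and 1.6 to 6.7 points at 67%. It is negligible with none or one, and smaller if the brow had already been fully treated.

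A reader might conclude that missing lifts in these subjects must count as no lift in the primary analysis. That would change the estimand to a composite failure and would bias the estimate downward if some partly treated subjects do lift. The documents do not require it.

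**What to change.** Reconcile 10.5.3 with 9.2.6.1 and 9.2.6.2 for outcome assessment only. State that every treated subject, including one whose session was stopped early, is asked to attend the scheduled Day 90 and Day 180 visits for photographs and FACE-Q, and is analysed in the ITT as observed. For a Stage 1 subject, Day 180 would still depend on reconsent.

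In SAP 6.1.1.2, add a sensitivity analysis that counts as no lift only those pain-stopped subjects whose Day 90 lift is still missing, with all other missing values imputed as planned.

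The cost is about one sentence in the protocol and one in the SAP. The visits are already scheduled. The primary estimate may come out slightly lower. No change to pain or treatment management is proposed.
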